- d. For multi-site studies for which the Yale PI serves as the lead investigator: n/a

The treatment interventions and assessment protocols are well-established and pose primarily low risks to participants. The DSMP for the proposed pilot RCT focuses on close monitoring by the PI in conjunction with an independent Safety Monitor. Excessive adverse events and/or any serious events (should they occur) will be reported promptly to the NIH and to the Yale School of Medicine IRB (Human Investigation Committee). Other (less serious) adverse events will be reported to the IRB periodically during regular reporting periods. In addition to the DSMP, the Yale IRB reviews all aspects of the study protocol (including progress and problems) minimally once per year.

Monitoring for the safety of participants and the integrity and quality of data will be the responsibility of the PI, the study team, and the Yale IRB (Human Investigation Committee).

The PI will be responsible for monitoring the safety of participants and the integrity and quality of data for the proposed pilot RCT, executing the DSMP, and complying with reporting requirements to the NIH and Yale IRB.

Qualifications and responsibilities of the Safety Monitor.

The Safety Monitor for this trial will be [name], MD, MPH. [name] is an Assistant Professor of Pediatrics in the section of General Pediatrics at Yale, and practices as a general pediatrician at the Yale Pediatric Primary Care Center. [name] is an experienced pediatrician with substantial clinical research and clinical expertise with adolescents and families, including those with obesity. [name] is not involved in the study design or clinical intervention or

related to any chain of command. As Safety Monitor, [name] will review the reports sent by the PI and will determine whether there is any corrective action, trigger of an ad hoc review, or stopping rule violation that should be communicated to the study PI, the IRB at the Yale School of Medicine, and the NIH.

Risk Assessment

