This is a behavioral (NON-medication) RCT that does not involve multiple sites, treatment blinding, or high-risk interventions. Although the pilot RCT does include vulnerable individuals (adolescents 12-17 years old), the risks associated with the proposed pilot RCT, including the cognitive-behavioral treatment and assessment protocols, are judged to pose minimal risks to participants. Therefore, we provide the following plan for monitoring the safety of participants and the integrity and quality of data:

Measurement and Reporting of Data Integrity and Quality

The PI is responsible for monitoring the data, assuring protocol compliance, and conducting the safety reviews. During the review process, the PI will evaluate whether the study should continue unchanged, require modification/amendment, or close to enrollment.

The PI, in consultation with [name] (Primary Mentor), will provide a summary of the DSMP report to the NIH as part of the annual progress report and to the Yale IRB on a yearly basis as part of the annual re-approval process. The DSMP reports will include Subject accrual, Treatment completion rates, Interim analyses, and Adverse and serious adverse events. These reports will be discussed with the mentoring team during regular meetings and sent to the Safety Monitor for review. The frequency of data review is summarized in the following table:

	Data Type	Frequency of Review by PI	Frequency of Review by PI and Safety Monitor
1	Subject accrual	Monthly	Annually
2	Treatment completion rates (retention/attrition)	Quarterly	Annually
3	Interim analyses	Twice Yearly	Annually
4	Adverse and serious adverse event rates	As needed	Annually
5	Checklist for Safety Monitor	NA	Annually

The PI, the Institutional Review Board (IRB) and/or the Safety Monitor have the authority to stop or suspend the study or require modifications.

Subject Accrual

Subject accrual reviews will help to assure that subjects are being enrolled (accrued) at a rate necessary to meet the recruitment goals in general and with regard to racial/ethnic diversity.

Subject accrual rates will be discussed with the PI monthly and annual accrual rates will be reported by the PI to the Safety Monitor to determine if any corrective action is needed to meet the recruitment goals.

Treatment Completion Rates

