Retention, attrition and completion rates will be carefully tracked and reviewed. This will be done quarterly to highlight any possible concerns and will be reviewed formally with the PI and Safety Monitor annually. Differential dropout across treatments and/or higher than expected dropout will be reviewed to determine whether any problems are present and what, if any, corrective action needs to be taken. "Trigger points" for corrective action, as described below, include: 35% ("low alert"), 40% ("mid alert"), 45% ("high alert"), and 50% ("extreme alert"). With early alerts to problems, action

would be taken to avoid higher level alerts; if a higher-level alert should arise, more drastic actions would be taken.

It is possible that baseline differences between the treatment conditions, excessive attrition, and/or missing data will limit the value of the data analysis, and hence knowledge to be gained from this study. For these reasons, interim analyses will be conducted twice yearly. Baseline differences, if present, will be considered in relation to potential effects on the power to detect differences in the primary outcomes. If these effects were to develop and be sizeable, alterations to the randomization schedule would be considered. Such effects would be evaluated and discussed by the PI and mentors, and plans would be communicated to the NIH and Yale IRB. To address excessive attrition and missing data, the following actions would be taken at the “trigger point” for each level of alert:

- 1) Low-level alert (35%): Review of potential problems by PI and review of procedures for supervision of study clinicians.
- 2) Mid-level alert (40%): Meeting between PI and senior study team members to discuss approaches to minimize further dropouts.
- 3) High-level alert (45%): Meeting between PI and senior study team members to determine further alterations to study protocol to complete the study with no further losses.
- 4) Extreme-level alert (50%): In the unlikely event that a 50% dropout rate occurs prior to the mid-study time point, the PI and senior study team members would convene to discuss the usefulness of continuing the study.

It is possible that other situations could occur that might warrant stopping the trial. Any concerns would be discussed with appropriate parties (PI, Mentors, Safety Monitor, NIH, Yale IRB).

Measurement and Reporting of Adverse Events

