Study participant safety will be monitored by the study team and reported to the PI at all visits and referrals will be provided if warranted and/or requested. If a study participant experiences any psychiatric symptoms or distress (e.g., depressive symptoms or suicidality) at any stage of study participation they will receive short-term treatment and support from the study treatment team (which includes psychologists) and will be connected to a local emergency department and their physician or therapist for ongoing care.

Other Potential Issues Relating to Stopping Rules for the Pilot RCT Include:

- 1) **New Information:** It is unlikely that any new information would become available during this trial that would necessitate stopping the trial. If new data become available, these will be evaluated.
- 2) **Limits of Assumptions:** It is possible that baseline differences between the treatment conditions, excessive attrition, and/or missing data could limit the value of data analysis. Baseline differences across treatment groups, if present, will be evaluated twice yearly and considered in relation to potential effects on the power to detect differences in the primary outcomes. If these effects were to develop and be sizeable, alterations to the randomization schedule would be considered. Any plans to alter the randomization scheme would be communicated to the NIH.
- 3) **Limits of Rules:** There are other situations that could occur that might warrant stopping the trial and/or including a section on the safety report entitled “Other situations that have occurred since the last safety report that warrant discussion” to allow for communication of concerns.

13. **Statistical Considerations:** Describe the statistical analyses that support the study design.

DATA ANALYSIS AND AIMS

Baseline demographic and clinical characteristics will be compared between treatment and control groups using chi-square tests for categorical variables (e.g., sex) and ANOVAs or Kruskal-Wallis tests for continuous variables (e.g., BMI z-score). Continuous variables will be examined for adherence to normality using probability plots and Kolmogorov-Smirnov tests. If normality is not satisfied and transformations do not achieve acceptable normality, alternative strategies (e.g., nonparametric) will be considered. Dropouts and completers will also be compared. Analyses will be intent-to-treat. Outcomes will be tested at the $\alpha=0.05$ threshold.

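### The monitoring plan leaves open an undefined mid-trial change to the randomization schedule, which could weaken concealment and recover little power that baseline adjustment would not

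*Combined protocol and SAP*

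**What the plan says.** The provision appears twice in Section I, item 12. Under Treatment Completion Rates, the concern is the effect of baseline differences on power: "Baseline differences, if present, will be considered in relation to potential effects on the power to detect differences in the primary outcomes". The next sentence is "If these effects were to develop and be sizeable, alterations to the randomization schedule would be considered". The reviews are frequent ("For these reasons, interim analyses will be conducted twice yearly"), and the route for a decision is "Such effects would be evaluated and discussed by the PI and mentors, and plans would be communicated to the NIH and Yale IRB". The Limits of Assumptions item, under the stopping-rule issues, repeats the provision and adds "Any plans to alter the randomization scheme would be communicated to the NIH".

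Four other places bear on it. The Risk Assessment says the trial "does not involve multiple sites, treatment blinding, or high-risk interventions". The data-review table has the PI review interim analyses twice yearly. Item 9 gives the PI the final eligibility decision. Item 13 (Overall analysis strategy) lists time, treatment, their interaction and random subject effects; it names no baseline covariates and does not say how the baseline value of the outcome is handled. Table 2 collects both primary outcome measures, QEWP-5 and BMI z-score, at baseline.

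Oversight exists: "the Yale IRB reviews all aspects of the study protocol (including progress and problems) minimally once per year", and "The PI, the Institutional Review Board (IRB) and/or the Safety Monitor have the authority to stop or suspend the study or require modifications".

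**The concern.** Neither the trigger nor the action is defined. The text does not say which baseline variables count, how large a difference is needed, or whether the change would be to the ratio, the blocks, stratification or minimization. The same section gives dropout four numeric triggers (35%, 40%, 45% and 50%), each with its own action.

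The person who would weigh the imbalance, with the mentors, also decides who enters an unblinded trial. The document says participants are randomly assigned but describes neither a concealment procedure nor who holds the schedule. A change made in response to observed differences between arms could make coming assignments easier to anticipate, or invite choices about who is enrolled next. Selection bias of that kind cannot be reliably removed in the analysis. A chance imbalance in a measured covariate can be, provided the model truly adjusts for it. The question is whether the power the option might recover justifies the risk.

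**Working it through.** **Inputs.** From the power paragraph of item 13: 25 per arm, d=0.8, two-sided alpha 0.05; with 20% dropout, 20 per arm and d=0.9; 80% power in both cases. The baseline imbalance D (in SD) and the covariate-outcome correlation ρ are assumptions, because the document gives neither. Power uses the noncentral t distribution unless stated.

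**1. The plan's own figure.** SE = √(1/25 + 1/25) = 0.2828, noncentrality 0.8/0.2828 = 2.828, 48 df: power 79.1% (80.7% by normal approximation). For 20 per arm and d=0.9: 79.2% (81.2%). The stated 80% reproduces.

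**2. If the alteration is a change of ratio.** SE = √(1/n₁ + 1/n₂). At 30:20, SE = 0.2887 and power is 77.5%; at 33:17 it is 74.7%. With 40 participants and d=0.9, 24:16 gives 77.6% against 79.2%. This applies to moving away from 1:1. Returning from 30:20 to 25:25 would regain the same 1.6 points.

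**3. If it aims at covariate imbalance and the analysis adjusts.** The most an alteration can recover is what the imbalance costs. For a single-endpoint ANCOVA with n per arm, SE = √{(1−ρ²)[2/n + D²/(2(n−1))]}, df = 2n−3. With n=25 and d=0.8:

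| D | ρ=0 | ρ=0.3 | ρ=0.5 | ρ=0.7 |
|---|---|---|---|---|
| 0 | 79.1% | 82.7% | 89.2% | 97.3% |
| 0.25 | 78.5% | 82.1% | 88.7% | 97.0% |
| 0.5 | 76.6% | 80.3% | 87.3% | 96.4% |
| 0.8 | 72.7% | 76.7% | 84.2% | 94.9% |

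The loss at D=0.5 is 2.6, 2.4, 2.0 and 0.9 points; at D=0.8 it is 6.4, 6.1, 5.1 and 2.4. By chance a single covariate exceeds 0.5 SD in about 8% of trials of this size, and 0.8 SD in about 0.5% (the SD of D is √(2/25) = 0.2828).

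**4. The same imbalance without adjustment.** If D=0.5 runs against CBT, conditional power is approximately 1 − Φ{[1.96√(2/n) − (d − ρD)] / √[(1−ρ²)·2/n]}.
- ρ=0.3: (0.554 − 0.650)/0.270 = −0.35, so 64%.
- ρ=0.5: (0.554 − 0.550)/0.245 = 0.02, so 49%.

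ANCOVA on the unchanged schedule gives 80.3% and 87.3% (step 3).

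**5. Baseline as an unconstrained time point.** With a free treatment difference at baseline, complete data and equal variances, the time-by-treatment contrast at post is a difference in change scores, with SE = √[2(1−ρ)·2/n].
- ρ=0.3: SE = 0.335, power 65% (ANCOVA 83%).
- ρ=0.5: SE = 0.283, power 79% (ANCOVA 89%).

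Nor does this contrast remove a chance imbalance. The adverse direction is now CBT starting at the better baseline value. Replacing ρD by (1−ρ)D and the test SE by the change-score SE in step 4:
- ρ=0.3: (0.656 − 0.450)/0.270 = 0.76, so 22%.
- ρ=0.5: (0.554 − 0.550)/0.245 = 0.02, so 49%.

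Exact t-based values for the conditional figures in steps 4 and 5 are up to about two points lower.

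**The case against.** The best opposing argument is that imbalance can cost far more than two or three points. Step 4 shows this for an unadjusted comparison and step 5 for a change-score contrast, and item 13 names no baseline covariates. This stands, and it limits the claim: the option recovers little that baseline adjustment would not. It does not rescue the option, because adjustment on the unchanged schedule restores the power in those cases.

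Second, the clause is a contingency in a pilot, with plans communicated to the NIH and, in one of the two places, the IRB. The IRB reviews the protocol at least yearly, and the IRB and Safety Monitor can require modifications. That also stands, and it lowers the urgency. It supplies neither a threshold nor a defined alteration.

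Third, stratification or minimization run by an independent person need not reveal coming assignments, and the missing description of concealment is the more basic gap. Both are fair. The document does not say that any alteration would be run that way.

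A reader might infer that concealment has been or will be broken, or that the trial has a planned adaptive randomization. The documents support neither. A change would only be considered, and they do not say who generates or holds the schedule or whether the PI can see it.

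**Conclusion.** The concern holds in a limited form. The protocol twice keeps open a data-driven alteration of the schedule with no defined trigger or form, in an unblinded trial whose PI reviews interim analyses and decides eligibility. The risk to concealment is an inference from those roles, and its size cannot be computed because the alteration is not described.

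Against baseline adjustment on the unchanged schedule, the power at stake is small: 0.9 to 2.6 points for a 0.5 SD imbalance, and up to 6.4 points for a rare 0.8 SD imbalance. These figures assume D and ρ and a single-endpoint ANCOVA, not the planned mixed model.

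The broader reading, that baseline imbalance hardly matters for power whatever the analysis, is not supported; it fails for unadjusted and change-score analyses. Nor does every ratio change lower power, since that is true only of moving away from 1:1. Importance is between optional and recommended, with medium confidence.

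**What to change.** In item 12, in both Treatment Completion Rates and Limits of Assumptions, replace the alteration sentence with: *The randomization schedule will not be altered in response to observed baseline differences; these are addressed by the prespecified baseline adjustment in Section 13.* Remove the Limits of Assumptions sentence on telling the NIH of plans to alter the scheme, and confine the corresponding Treatment Completion Rates sentence to other plans. If enrolment has begun, follow the existing schedule to its end and report whether it was ever altered.

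In item 13, state that each primary outcome model adjusts for the baseline value of that outcome (QEWP binge/LOC frequency; BMI z-score). Use either a baseline covariate with post-baseline responses only, or baseline as a response with its mean constrained equal across arms; do not use an unconstrained time point. Name a short list of any other prognostic covariates before the outcome analysis, without reference to differences between arms.

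The twice-yearly reviews, dropout alerts and oversight powers stay as they are. No participants, visits or measures are added. The team gives up the option to rebalance, and a covariate unrelated to outcome costs a little power (79.1% to 76.6% at a 0.5 SD imbalance), which is why the list should be short.

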Overall analysis strategy. Descriptive statistics will quantify change and mixed-effects models (106, 107) will compare treatments through post; 3-month follow-up will be exploratory. These models allow for different numbers of observations per participant, use all available data on each participant, account for clustered data observations, and are unaffected by data missing at random. A further advantage is the capacity to test and account for individual-difference contributions to treatment outcomes (108). This strategy provides flexibility in modeling the correlation structure of the data. In models for each outcome, we will include fixed effects of time and treatment and their interaction, and random subject-level effects. Because we cannot *a priori* predict the shape of the response over time, we will first treat time as categorical and then test for polynomial trends. We will consider different error structures (e.g., compound symmetry, autoregressive) and select the best-fitting structure based on information criteria. Data on all participants enrolled in the study will be used in mixed models. We will compare dropout patterns and if there are concerns of informative dropout and/or informative intermittent missing data, we will use pattern mixture models to perform sensitivity analyses to main analyses.

Primary Aims.

Primary Aim 1 is to **test** the efficacy of adolescent CBT relative to the active control condition at post-treatment on clinical outcomes, including: (a) reduction in binge/LOC eating frequency (evaluated by the QEWP), and (b) reduction in weight (evaluated by BMI z-score). Significant time-by-treatment effects with significantly less adolescent binge/LOC eating and significantly reduced weight in adolescent CBT relative to the control condition will be considered supportive of these aims. Parallel analyses will also assess binge/LOC frequency reduction using the EDE; because this interview is only administered at baseline and post, this analysis will, by definition, occur among completers. Adolescent CBT is hypothesized to yield reduced binge/LOC eating frequency and weight reduction (i.e., weight loss or less excess weight gain) compared to the control group.

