Primary Aim 2 is to **test** the acceptability and establish the feasibility of adolescent CBT. Descriptive statistics will quantify clinician/patient treatment ratings, sessions attended, and retention, and clinician adherence/competence through ratings of recorded sessions.

Secondary Aims.

Secondary Aim 1 is to **explore** the efficacy of adolescent CBT relative to active control: (a) reduction in disordered eating thoughts and behaviors (EDE-Q), (b) improvements in executive function (S-Upps, Kirby), (c) improvement in psychosocial functioning (reduced depression, PHQ; improved self-esteem, RSES).

Secondary Aim 2 is to **explore** the durability and maintenance of treatment effects during short-term follow-up.

Secondary Aim 3 is to **explore** potential predictors of primary outcomes. Following Kraemer's (109) conceptual/statistical model for predictors, we will explore whether baseline characteristics predict treatment effects by testing for main effects and interactions in models for primary outcomes (specified above), including (a) adolescent executive function (S-Upps, Kirby), (b) self-weighing (EARLY), (c) parent BMI and disordered eating behaviors (EDE-Q/QEWP), and (d) parent feeding practices and attitudes (CFQ). [name] et al (25) used this analytic strategy in earlier work.

Power Analysis and Justification of Sample Size. Results are anticipated to yield significant impact by providing effect sizes for grant applications to perform definitive studies comparing the new adolescent CBT treatment with existing interpersonal therapy for youth LOC. Power estimates for the pilot RCT were based on the comparison of CBT (n=25) and control conditions (n=25). Assuming a two-sided test at $\alpha=0.05$ threshold, we have 80% power to detect clinically meaningful between-subjects ($d=0.8$) and within-subject effects within each group ($d'=0.58$). Even assuming 20% dropout, we still have 80% power to detect clinically meaningful effects ($d=0.9$ between-subjects and $d'=0.66$ within-subject). While power is limited given the pilot nature of the study, such effects are similar to effects observed in a prior study (31) that compared LOC eating between youth who received either interpersonal therapy or were in a control group. Thus, we have a reasonable chance of finding statistically significant differences between CBT and control, even in this pilot study.

SECTION II: RESEARCH INVOLVING DRUGS, BIOLOGICS, RADIOTRACERS, PLACEBOS AND DEVICES
--

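### Do the attrition alerts, which start at 35%, leave dropout between 20% and 35% unguarded?

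*Combined protocol and SAP*

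**What the plan says.** Section I, item 13 (Power Analysis and Justification of Sample Size) gives power for two cases. With 25 per arm the trial has 80% power for d=0.8. The second case reads "Even assuming 20% dropout, we still have 80% power to detect clinically meaningful effects", with d=0.9 between arms. No larger loss is considered.

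Section I, item 12 (Treatment Completion Rates) sets four trigger points: 35%, 40%, 45% and 50%. The first is "Low-level alert (35%): Review of potential problems by PI and review of procedures for supervision of study clinicians". The second is "Mid-level alert (40%): Meeting between PI and senior study team members to discuss approaches to minimize further dropouts". Apart from these numbers, the same section says that differential dropout and "higher than expected dropout will be reviewed to determine whether any problems are present and what, if any, corrective action needs to be taken". Completion rates are tracked quarterly and go formally to the Safety Monitor each year. Interim analyses run twice a year, and excessive attrition and missing data are among the reasons given for them.

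On analysis, item 13 says the mixed models "use all available data on each participant". For the EDE interview version of the binge/LOC outcome it says "because this interview is only administered at baseline and post, this analysis will, by definition, occur among completers".

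**The concern.** Read together, the two sections leave a gap of 35% − 20% = 15 percentage points, or 7.5 of 50 participants (10 lost against 17.5 lost). In that band the trial is outside the range for which power is stated, yet no numbered alert has sounded. The only wording that applies there refers to an expected rate that is never given, and the denominator of the percentages is not stated either. The meeting on how to limit further losses comes later still, at 40%. In a trial of 50, missing post-treatment data cannot easily be replaced. If the alerts are meant to be early warnings, a first alert at 35% looks late.

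**Working it through.** **Inputs from the protocol.** 25 per arm; two-sided alpha 0.05; dropout scenario 20%; triggers 35%, 40%, 45%, 50%.

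**1. Reproduce the stated power.** Two-sample t-test with df = n1 + n2 − 2 and noncentrality d × √(n1·n2/(n1+n2)).

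- 25 per arm, d=0.8: 0.8 × √12.5 = 2.83 on 48 df; power 79.1%.
- 20 per arm, d=0.9: 0.9 × √10 = 2.85 on 38 df; power 79.2%.

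Both agree with the stated 80% after rounding.

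**2. Extend the same calculation past 20%.** Completers = 50 × (1 − loss), split evenly between arms.

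| Loss | Completers per arm | Power at d=0.9 | d detectable at 80% power |
|---|---|---|---|
| 20% | 20 / 20 | 79% | 0.91 |
| 30% | 18 / 17 | 73% | 0.98 |
| 35% | 16.25 / 16.25 | 70% | 1.02 |
| 40% | 15 / 15 | 66% | 1.06 |

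**3. Allow for the planned mixed model.** The protocol gives no correlation and no dropout timing, so these are assumptions: five visits to post; compound-symmetry or AR(1) correlation of 0.3 to 0.8; dropout missing at random; timing from all early to all late. The information on the baseline-to-post time-by-treatment contrast is scaled so that no loss equals 25 per arm.

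| Loss | Effective n per arm | Power at d=0.9 |
|---|---|---|
| 20% | 20.4–23.2 | 80–85% |
| 35% | 16.8–21.5 | 72–82% |
| 40% | 15.6–20.8 | 68–81% |

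The ranges at 20% and 35% overlap.

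**4. How often would a trial end in the band?** Assume true dropout of 30%; the protocol gives no rate. With X ~ Binomial(50, 0.30), P(11 ≤ X ≤ 17) = 0.70 and P(X ≥ 18) = 0.22. If the rate to date is checked at every 10 participants, with each participant's status known at the check, 35% is reached at some check with probability 0.56, or 0.49 if checks begin at 20 participants. Varying the first check (5 to 20) and the spacing (2 to 10) moves this to 0.46–0.71.

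**5. How would an alert just above 20% behave?** Same checks, firing when the rate to date exceeds 20%:

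- True dropout 20%: fires at some check with probability 0.58–0.62. At the end of the trial, P(X > 10) = 0.42.
- True dropout 15%: fires at some check with probability 0.26–0.32.

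**6. What already operates below 35%.** Items 12 and 13 serve different purposes: the 20% in item 13 tests how far power holds, and the percentages in item 12 are escalation steps for excessive attrition. With no 35% floor, item 12 provides quarterly review of completion rates by the investigator, review of differential or excess dropout with possible corrective action, twice-yearly interim analyses, and a Safety Monitor who may call for corrective action or an ad hoc review. The action at 35% is a review by the investigator plus a look at supervision procedures. Moving it to 20% would mostly rename the quarterly review.

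**The case for a change.** The best case for a change starts from the plan's own reasoning. Item 12 says that excessive attrition can limit what the analysis is worth, and that early alerts should head off later ones. On the plan's own power basis, a first alert at 35% comes after power at d=0.9 has dropped to 70%. A review keyed to an unstated expectation cannot be shown to have been triggered or missed. The EDE analysis is confined to completers, so the full loss applies to it. Rewording would cost little.

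Some of this stands. No expected rate is given, the denominator is missing, and the text does not say whether the percentage counts participants who stop treatment or those who miss the post assessment. Under intent-to-treat analysis these need not be the same people. They are gaps in detail that the study team can settle when it compiles its quarterly figures.

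The rest does not carry a change. Nothing in the protocol makes 20% the expected rate, so defining excess dropout by it would give that figure a role the plan never assigned. The EDE analysis runs parallel to the primary QEWP analysis. An earlier team meeting is the one step that would alter conduct, and nothing in the documents fixes where it should fall.

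**Conclusion.** The description is accurate: stated power ends at 20% dropout, numbered alerts begin at 35%, and expected dropout has no figure. It is not an error. No stated power figure is wrong, the two percentages answer different questions, and losses between them are reviewed under other provisions of the same monitoring plan. Where to set escalation steps is a judgement. The current choice trades a later formal alarm against fewer false ones, and the mixed-model analysis remains sound either way.

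The size of the issue is a fall in power at d=0.9 from 79% to 70% between 20% and 35% loss on completer counts, and from 80–85% to 72–82% for the mixed model. The completer figures assume equal loss in both arms. The mixed-model ranges rest on the assumed correlations and dropout timing, and the probabilities of ending in the band rest on an assumed 30% rate. The protocol already says that power is limited in a pilot of this kind. A sentence giving the expected rate, what is counted and the denominator would be a courtesy to readers; the plan does not depend on it.
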